11.2.2. Definition of an Adverse Reaction

An adverse reaction means any AE caused by a drug.

11.2.3. Definition of a Suspected Adverse Reaction

A suspected adverse reaction means any AE for which there is a reasonable possibility that the drug caused the AE. The term, “reasonable possibility” means that there is evidence to suggest a causal relationship between the drug and the AE. A suspected adverse reaction implies a lesser degree of certainty about causality than the term, “adverse reaction.”

11.2.4. Definition of a Serious Adverse Event

An SAE is an AE that results in any of the following outcomes:

- Death;
- A life-threatening AE (i.e., if in the view of the investigator or sponsor, the subject was at immediate risk of death at the time of the event. Life-threatening does not include an event that, had it occurred in a more severe form, might have caused death);
- Inpatient hospitalization or prolongation of existing hospitalization;
- A persistent or significant incapacity or substantial disruption of the ability to conduct normal life functions;
- A congenital anomaly or birth defect; or
- Is an important medical event (based on appropriate medical judgment, the event jeopardizes the subject and may require medical or surgical intervention to prevent one of the above-listed outcomes).

11.3. Procedures for Eliciting, Recording, and Reporting Adverse Events

11.3.1. Adverse Event Reporting Period

The study period during which all AEs and SAEs must be reported begins after informed consent is obtained and ends 28 days after the last treatment.

Adverse events will be followed until resolved, stable, or until the subject's last study visit. If an AE is not resolved or stabilized at the subject's last visit, it is up to the discretion of the investigator and study medical monitor to determine if further monitoring of the event is warranted.

Adverse events collected prior to dosing of study drug will be considered "treatment non-emergent" while those reported after the first dose of study drug will be considered "treatment emergent" and be assessed for relationship to study drug.

During the AE reporting period, study site personnel will query each subject at each visit to actively solicit any AE occurring since the previous visit. This does not preclude the site from collecting and recording any AEs reported by the subject to site personnel at any other time.

11.3.2. Assessing Adverse Event Severity

The investigator should use the National Cancer Institute Common Terminology Criteria for Adverse Events (NCI CTCAE v4.0), which may be found at:

http://ctep.cancer.gov/protocolDevelopment/electronic_applications/ctc.htm#ctc_40

This will serve as guidance for specific severity assessment criteria.

The NCI CTCAE provides a descriptive terminology used for AE reporting and severity grading. It is a comprehensive dictionary of medical terms that facilitates accurate and consistent medical coding. It does not contain every event that may occur in a given study. Adverse events that are not covered by the NCI-specific criteria will be assessed for severity using the following criteria:

- Grade 1: Mild; asymptomatic or mild symptoms; clinical or diagnostic observations only; intervention not indicated.
- Grade 2: Moderate; minimal, local or noninvasive intervention indicated; limiting age-appropriate instrumental activities of daily living (e.g., preparing meals, shopping for groceries or clothes, using the telephone, managing money).
- Grade 3: Severe or medically significant but not immediately life threatening; hospitalization or prolongation of hospitalization indicated; disabling; limiting self-care activities of daily living (e.g., bathing, dressing and undressing, feeding self, using the toilet, taking medications, and not bedridden).
- Grade 4: Life-threatening consequences; urgent intervention indicated.
- Grade 5: Death related to AE.

11.3.3. Assessing Relationship of Adverse Event to Study Drug

Most of the information about the safety of a drug prior to marketing comes from clinical trials; therefore, AE reports from investigators are critically important. Moreover, appropriately deciding whether the AE meets the definition of a suspected adverse reaction is usually the most difficult determination, but it is critical to avoid the miscategorization of the product's safety profile.

Due to the historical tendency for assessment of relationship to default as possibly related, the FDA has issued new guidance that clarifies the intent of the phrase "reasonable possibility" in the definition of "associated with the use of the drug." Default reporting of individual events as "possibly related" is uninformative and does not meaningfully contribute to the development of the product safety profile.

The investigator must provide an assessment of the relationship of the AE to study drug in accordance with the guidance below. Absence of an alternative cause would not normally be considered enough evidence to assess an event as "possibly related" or "related" to study drug.

Related (Adverse Reaction):

- Any event for which there is evidence to conclude that the study drug caused the event.

Possibly Related (Suspected Adverse Reaction):

- A single occurrence of an event that is uncommon and known to be strongly associated with drug exposure, such as angioedema, anaphylaxis during infusion, rhabdomyolysis, Stevens-Johnson syndrome, etc.
- One or more occurrences of an event that is not commonly associated with drug exposure but is otherwise uncommon in the population exposed to the drug, such as tendon rupture.

Not Related:

- The event represents the underlying disease (e.g., disease-related symptoms, disease progression)

- The event represents a comorbid condition present at the time the subject entered the study
- The event represents a known adverse reaction associated with a co-medication received by the study subject
- The event is common for the study population (e.g. cardiovascular events in an elderly population)
- The event has no plausible relationship to study drug
- The event is a study endpoint (e.g., mortality, major morbidity)

The investigator must provide an assessment of the relationship of the event to study drug, as this information is very important to monitor the real-time safety of the study drug. However, as the manufacturer of the study drug, FibroGen is responsible for making the final causality assessment for individual reports, and for reporting suspected adverse reactions and adverse reactions to Health Authorities.

In order to support this practice, FibroGen will perform periodic aggregate data reviews to assess for: 1) one or more occurrences of rare/uncommon AEs, and; 2) increases in the observed frequencies of AEs that would be expected for the underlying disease and study population.

While the investigator must provide an assessment of the relationship of the event to study drug, in most cases only aggregate data review will be used to make the determination of the relationship of the study drug to a given AE. This information will be updated periodically and provided in the IB.

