1.6.3. Safety

The overall frequency and type of treatment-emergent adverse events (TEAEs) and serious adverse events (SAEs) observed in these clinical studies reflect events that would be expected to occur in CKD subjects with multiple co-morbidities and on a number of concomitant medications. There has been no SAE attributable by the sponsor to the use of roxadustat. Safety analyses did not reveal any association between the rates of occurrence of cardiovascular events with roxadustat, or any effect on AE rates related to either increasing Hb levels or on the rate of change of Hb levels.

Adverse event rates of hypertension (1% in Study FGCL-SM4592-017, 7.6% in Study FGCL-4592-041, and 10% FGCL-4592-053) and serious adverse events of arteriovenous-fistula thrombosis (overall incidence in dialysis-dependent CKD subjects: 2%), compare favorably with the rates reported in published ESA studies in similar subject populations (Krapf and Hulter 470-80; Fishbane and Besarab 1274-82). No safety risks were associated with increased rate of rise of Hb levels or with achieving a Hb level above 11 g/dL using roxadustat. Although Study FGCL-4592-041 subjects achieved Hb > 11 g/dL in 52% of exposure time during study, no cardiovascular safety events (death, MI, stroke, unstable angina, hospitalization for congestive heart failure, or hospitalization for arrhythmias) were reported while Hb > 11 g/dL during treatment with roxadustat.

No increased cancer risk has been noted with roxadustat treatment; however, the study program was not powered to detect absence of cancer risk.

Liver enzymes were monitored closely throughout the roxadustat clinical development program. Increases in liver enzymes were infrequently seen, and were generally mild and transient in nature. No cases of Hy's Law were observed throughout the program. An independent data and safety monitoring committee concluded that there was no concern for hepatotoxicity with roxadustat.

Based on the safety data collected to date, roxadustat has an acceptable safety profile that supports its further development.

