3 STUDY DESIGN

This is an open-label, long-term maintenance study of roxadustat anemia therapy in dialysis and non-dialysis subjects with CKD who completed the treatment period of a Phase 2 roxadustat anemia study in the U.S.

Subjects who received roxadustat in a previous study continued to receive roxadustat at the same dose and frequency as they received at the end of the treatment period in their previous study, unless a dose adjustment was required, at time of switching over to this study. Roxadustat was supplied in an open-label manner to all subjects.

This study (amendment 2) accommodated the potential for prior study participants on a placebo, to switch to this study: Subjects who received placebo in their previous study could start treatment with roxadustat at starting doses according to their weight (Appendix B of the protocol). Planned total study duration was up to 312 weeks (6 years), including up to an additional 1 year under Amendment 2.

Study visits were scheduled every 2 weeks, for the first 104 weeks (2 years) of study drug treatment (time on the previous Phase 2 studies of roxadustat), followed by every 4 weeks until the end of the treatment period.

After the end of treatment (defined as the last day a subject receives study drug) the subjects returned for a follow-up visit 4 weeks later.

The baseline Hb value for efficacy analysis is defined as the mean of the central laboratory Hb value from the baseline visit at Day 1 (prior to receiving the first dose of study drug in this study), plus any other central lab Hb values within 15 days prior to Day 1.

Safety is assessed by vital signs, physical examinations, clinical laboratory values (serum chemistries including liver function tests [LFTs] and complete blood counts [CBC]), electrocardiograms (ECGs), AEs and concomitant medication reporting. Clinical laboratory tests, including LFTs and Hb levels, could y be assessed at additional times on unscheduled visits for safety reasons.

Fifteen subjects entered this study: 1 subject from FGCL-4592-040 and 14 subjects from FGCL-4592-041. All subjects received Roxadustat prior to entering this study (0 subject received placebo). Descriptive analyses will be performed for all subjects.

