11 SAFETY ANALYSES

11.1 ADVERSE EVENTS

An AE (classified by preferred term) occurring after the first dose of study medication and up to the last dose of study medication +28 days is considered a treatment emergent adverse event (TEAE) if it was not present prior to the first dose of study medication, or it was present prior to the first dose of study medication but increased in severity during the treatment period.

The number and percentage of subjects reporting TEAEs are tabulated by system organ class and preferred term. If more than one event occurs with the same preferred term for the same patient, the patient is counted only once for that preferred term using the most severe and most relatedness occurrence for the summarization by severity and by relationship to the study medication. In addition to the frequency tables above, crude event rate are provided. The crude event rate of interest (per 100 patient exposure years) by system organ class and preferred term is calculated as: number of the events per PT and SOC / total patient exposure years (PEY)*100.

The following TEAE table and listings are provided.

1. TEAE by system organ class and preferred term
2. TEAE by system organ class, preferred term, and maximum severity
3. TEAE by system organ class, preferred term, and relationship to study medication
4. Treatment-emergent serious AEs (TESAE) by system organ class and preferred term
5. TEAEs leading to discontinuation of study medication or from the study will be summarized by preferred term and treatment group
6. Listing of subjects with serious adverse events (SAEs)
7. Listing of subjects with adverse events leading to discontinuation of study medication or from the study

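### Protocol 11.3.3 lets investigators call worsening of a condition that began on roxadustat in the parent study 'Not Related', because the criterion is tied to entry into this extension

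*Protocol*

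**What the plan says.** Protocol 11.3.3 makes its causality categories binding on the site: "The investigator must provide an assessment of the relationship of the AE to study drug in accordance with the guidance below". Under the heading for unrelated events, one ground is that "The event represents a comorbid condition present at the time the subject entered the study". No exception is made for a condition that arose during earlier roxadustat treatment.

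The same section defines the related category as "Any event for which there is evidence to conclude that the study drug caused the event". It does not say which category prevails when an event fits both. Later in the section, the sponsor is made responsible for the final causality assessment of individual reports, mostly through aggregate review.

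On who enrolled, SAP 3 states: "Fifteen subjects entered this study: 1 subject from FGCL-4592-040 and 14 subjects from FGCL-4592-041". It adds: "All subjects received Roxadustat prior to entering this study (0 subject received placebo".

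SAP 11.1 plans, among other outputs, "TEAE by system organ class, preferred term, and relationship to study medication". It counts a condition present before the first extension dose as treatment-emergent if it became more severe during treatment.

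**The concern.** Presence at study entry is a reasonable argument against a drug cause when entry comes before first exposure. In a roll-over it does not. A condition that started on roxadustat in Study 040 or 041 and persisted to the roll-over is, on the wording of the criterion, a comorbid condition present at entry. If it then worsens or leads to a complication on continued roxadustat, the investigator has a listed reason to record it as unrelated, even though the whole course of the condition took place after first exposure.

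Long-term safety is part of the primary objective (Protocol 2.1). The by-relationship table is where a reader would look for events that investigators attributed to the drug. The criterion can only supply reasons for the unrelated column, so any misclassification through it runs in one direction, towards a more favourable picture.

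**Working it through.** The plan gives no figure for this point other than the enrolment count, so the check is that count followed by a comparison of the texts.

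**Step 1. Who was drug-free at entry?** Inputs from SAP 3: 1 subject from Study 040, 14 from Study 041, 0 from placebo.
- Total: 1 + 14 = 15, which agrees with the stated fifteen.
- Already exposed to roxadustat: 15 − 0 = 15, or 15/15 = 100%.

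Study entry is therefore a drug-free reference point for none of the subjects analysed.

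**Step 2. Does an on-drug condition fit the criterion?** Take a condition with onset after the first roxadustat dose in the parent study, still present at roll-over and worse in the extension.
- Protocol 11.3.3, unrelated list: it is comorbid and was present at entry, so the ground fits.
- Protocol 11.3.3, related category: it fits only if there is evidence sufficient to conclude that the drug was the cause. The section adds that lack of another explanation would not normally be enough.
- Precedence: none is stated. Both labels are open, and the unrelated one is easier to satisfy.

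**Step 3. Where does the label go?** In SAP 11.1:
- Affected: the table by system organ class, preferred term and relationship.
- Not dependent on the label: the overall table, the table by maximum severity, the serious-event table, the discontinuation summary, the listings, and the crude rates per 100 patient-exposure-years. The worsened condition counts as treatment-emergent in these.

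**Step 4. Does anything correct a recorded label?**
- SAP 13.5 imputes a related causality only when the field is missing, so it does not touch a recorded entry.
- The sponsor's aggregate review in Protocol 11.3.3 looks for increases in events expected for the disease and population. Protocol 4.1.1 provides no control group, and there are 15 subjects, so the review has no concurrent comparator within this study.

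**Step 5. Size.** The quantity needed is the number of subjects with a condition that began on roxadustat in the parent study, persisted to entry, worsened here, and was labelled unrelated on this ground. None of these components is given. The number lies somewhere from 0 to 15, and the documents narrow it no further. All entered subjects are analysed (SAP 5.1), so one subject moved between columns changes a percentage by 1/15 = 6.7 points. That is the resolution of the table, not an estimate of bias.

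**The case against.** The strongest reply is that the investigator's label is neither forced nor final. The related category remains available wherever there is evidence of causation, including evidence from the parent study. The sponsor makes the final assessment. The worsening itself stays visible in every other adverse event output. The protocol also provided for placebo roll-overs, for whom study entry does precede first exposure; that none enrolled is known only from the SAP. All of this stands, and it confines the problem to one table and one label. It does not remove it, because nothing in the plan corrects or marks an unrelated label that was given on the entry-date ground.

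Three stronger readings are tempting and are not supported.

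- *That events from carried-over conditions are unrelated by rule.* The criterion covers comorbid conditions, competes with the related category, and has no stated priority over it.
- *That the hypertension rate in Protocol 1.6.3 ("7.6% in Study FGCL-4592-041") sizes the problem.* Applied to the 14 subjects from that study, it gives 14 × 0.076 = 1.06 expected cases and 1 − 0.924^14 = 0.669 for at least one. But it is an adverse event rate. It does not say whether the hypertension was new on drug, persisted to roll-over or later worsened, and subjects who rolled over are a selected group. Hypertension could also be labelled unrelated under a separate ground in 11.3.3, that the event is common in the study population, so changing the entry date would not settle that example.
- *That Protocol 11.3.1 leaves a gap in assessment between consent and first extension dose* ("Adverse events collected prior to dosing of study drug will be considered" non-emergent). Multiplying 15 subjects by the 4-week consent limit in Protocol 7.1.1.1 gives 60 subject-weeks, but only as a ceiling. Actual consent dates and the share of that time on drug are not stated. The period may also overlap adverse event reporting in the parent study, whose protocol is not available here. A gap is not established.

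**Conclusion.** The concern holds in a limited form. The criterion in Protocol 11.3.3 uses a reference date that was drug-free for none of the 15 subjects. It permits, but does not require, worsening of a condition that began on roxadustat to be labelled unrelated. The consequence is a possible one-directional bias, in the drug's favour, in the SAP 11.1 by-relationship table. Its size cannot be computed from the documents.

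The conclusion rests on two points: investigators apply the listed grounds as written, as the section asks of them, and at least some conditions that arose on roxadustat in the parent studies were still present at roll-over. The first is a matter of text; the second is an assumption that the parent-study data could confirm or refute. In an uncontrolled, descriptive study this is a matter of interpretation that is cheap to correct. It does not undermine the safety data as a whole.

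**What to change.** **Protocol 11.3.3.** Replace the closing clause of the comorbid-condition criterion, which refers to study entry, with: *before the subject's first dose of roxadustat in any study*. This works for both kinds of roll-over. For a subject coming from placebo, the first dose in any study is the first dose in the extension.

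**SAP 11.1.** SAP 3 describes enrolment as complete, so new protocol wording may not reach assessments already made. For those, use the parent-study adverse event data to flag each treatment-emergent event whose condition began on roxadustat in Study 040 or 041. Footnote the by-relationship table to say that an unrelated label for a flagged event may rest on the entry-date criterion and should not by itself be read as evidence of no relation. No recorded investigator assessment is altered.

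**Cost.** One clause in the protocol, one derived flag and one footnote. The flag needs a link to the parent-study adverse event data, which the documents do not say is already in place. Under the revised criterion, a few more events may be classed as possibly related or related.

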11.3.4. Reporting Serious Adverse Events on the SAE Report Form

All SAEs must be reported to FibroGen immediately.

To report an SAE, the investigator must e-mail or fax an SAE Report Form to FibroGen within 24 hours of becoming aware of the event. Follow-up reports must be submitted in a timely fashion as additional information becomes available.

For each SAE observed, the investigator should obtain all of the information available about the event, including (but not limited to): hospital discharge diagnoses, hospital discharge note, death certificate, appropriate laboratory findings (including autopsies and biopsy results), and clinical examinations (including radiological examinations and clinical consultations).

11.3.4.1. Reporting Serious Adverse Events to the Institutional Review Board/Ethics Committee

The investigator is responsible for notifying his/her Institutional Review Board (IRB) or Independent Ethics Committee (IEC) of SAEs in accordance with local regulations. FibroGen, or its safety representative, will provide to the investigator a copy of any expedited safety reports that it intends to file with a regulatory authority.

11.3.4.2. Deaths

For any death occurring during the subject's study participation, regardless of attribution, the investigator will report the death immediately to the study medical monitor.

The investigator should notify FibroGen of any death or other SAE occurring after a subject has discontinued or terminated study participation that may reasonably be related to the study.

The investigator must submit the SAE Report Form and complete the appropriate CRF page for the event that led to the subject's death. This includes death attributed to progression of anemia or CKD.

When reporting a death, the event or condition that caused or contributed to the fatal outcome should be recorded as the primary event term on the SAE Report Form.

